APPENDIX L. EUROQOL-5 DIMENSION (EQ-5D) QUESTIONNAIRE

Under each heading, please tick the ONE box that best describes your health TODAY

MOBILITY	
I have no problems in walking about	
I have slight problems in walking about	
I have moderate problems in walking about	
I have severe problems in walking about	
I am unable to walk about	
SELF-CARE	
I have no problems washing or dressing myself	
I have slight problems washing or dressing myself	
I have moderate problems washing or dressing myself	
I have severe problems washing or dressing myself	
I am unable to wash or dress myself	
USUAL ACTIVITIES (e.g. work, study, housework, family or leisure activities)	
I have no problems doing my usual activities	
I have slight problems doing my usual activities	
I have moderate problems doing my usual activities	
I have severe problems doing my usual activities	
I am unable to do my usual activities	
PAIN / DISCOMFORT	
I have no pain or discomfort	
I have slight pain or discomfort	
I have moderate pain or discomfort	
I have severe pain or discomfort	
I have extreme pain or discomfort	
ANXIETY / DEPRESSION	_
I am not anxious or depressed	
I am slightly anxious or depressed	
I am moderately anxious or depressed	
I am severely anxious or depressed	
I am extremely anxious or depressed	

•

•

	The best health you can imagine	
We would like to know how good or bad your health is TODAY.	_ 	100
This scale is numbered from 0 to 100.	Ŧ	95
100 means the best health you can imagine. 0 means the worst health you can imagine.		90 85
Mark an X on the scale to indicate how your health is TODAY.	1	80
Now, please write the number you marked on the scale in the box	ŧ	75
below.	-	70
	=	65
	+	60
	Ŧ	55
YOUR HEALTH TODAY =	-	50
	Ŧ	45
	-	40
	ŧ	35
	-	30
		25
	-	20
	Ŧ	15
	-	10
	ŧ	5
	_ ∓_	0
	The worst healt you can imagin	e e

5.11.	Handling of Laboratory Samples Out of Stability	33
6. S	UPPORTING DOCUMENTATION	34
6.1.	Appendix 1: Technical Specifications for Derived Variables	34
6.2.	Appendix 2: Study and Participant Characteristics	44
6.2.1.	Protocol Deviations	44
6.2.2.	Demographics and Disease Characteristics	44
6.2.2.1.	Demographics and Disease Characteristics (Bleeding)	44
6.2.2.2.	Medical/Surgical History and Baseline Physical Examination	46
6.2.3.	Prior and Concomitant Medications	46
6.3.	Appendix 3: Instrument Scoring Details	46
6.3.1.	Glasgow Coma Scale	46

6.3.2.	Utility-Weighted mRS	46
6.3.3.	EQ-5D-5L Health State Index Score Calculations	47
6.4.	Appendix 4: Additional Details on Statistical Methods	
6.4.1.	COVID-19 Vaccine Risk Assessment	
6.4.1.1.	Vaccination	
6.4.1.2.	Potential Risks and Mitigation Measures	
6.4.1.3.	Reason for Not Collecting COVID-19 Information	
6.5.	Appendix 5: Changes to Protocol-Planned Analyses	
6.6.	Appendix 6: List of Abbreviations	
7.	REFERENCES	

LIST OF TABLES

Table 1:	Objectives and Endpoints	8
Table 2:	Analyses Sets	.15
Table 3:	Attributes of Primary (Composite) Estimand	.18
Table 4:	AEs and SAEs	.27
Table 5:	Clinically Significant Laboratory Criteria	.43
Table 6:	Clinically Significant Vital Sign Criteria	.43
Table 7:	EQ-5D-5L US cTTO Value Set	.47

VERSION HISTORY

This statistical analysis plan (SAP) for Study 18-513 is based on Protocol Version 3.0, dated 05 Dec 2022.

SAP Version	Version Date	Change	Rationale
0.2	07 Jun 2022	Not applicable	Original version
1.0	30 Nov 2022	 Updated primary efficacy analysis to using one stratification factor Updated sensitivity analyses for the primary endpoint Updated the analysis for secondary endpoint Updated analyses for correlation between effective hemostasis and anti-fXa activity Updated subgroup analysis Updated language in the section for interim analysis for better clarification Updated definition for the per protocol set 	Changes are made to align with the Protocol Amendment V3 and to incorporate comments from regulatory agency review
1.1	17 Apr 2023	 Added clarification of two data cutoff (DCO) points Added definition of screened set 	Changes are made to clarify the data used for the interim analysis, and the final analysis; and to differentiate the screened participants from the enrolled participants.

APPROVAL SIGNATURES

		20-Apr-2023 11:02 EDT
	, Alexion	Date dd Mmm yyyy
		20-Apr-2023 10:53 EDT
	, Alexion	Date dd Mmm yyyy
		21-apr-2023 12:43 IST
AstraZeneca	, ,	Date dd Mmm yyyy

1. INTRODUCTION

This statistical analysis plan (SAP) describes the statistical methods and outputs for analyzing data for Protocol 18-513, titled "A Randomized Clinical Trial of Andexanet Alfa in Acute Intracranial Hemorrhage in Patients Receiving an Oral Factor Xa Inhibitor." Standard data presentation instructions and table, figure, and listing specifications are contained in the Data Presentation Plan in a separate document.

All events and analyses occurring by Day 30 will be described in a primary clinical study report. Additional events and analyses for the period between Day 30 and Day 120 (if applicable) will be described in a safety follow-up clinical study report. All analyses and outputs described in this document are for the primary clinical study report.

1.1. Objectives and Endpoints

The overall objective of the study is to gain direct insights regarding the efficacy and safety of andexanet in Factor Xa (FXa)-anticoagulated participants with acute intracranial hemorrhage (ICrH).

The objectives, endpoints, and analysis population for each endpoint are summarized in Table 1. Attributes of the estimates for the primary efficacy analyses are found in Section 5.3.1.

Objectives	E	ndpoints
Primary Efficacy		
• Evaluate the effect of and versus usual care on the ra effective hemostasis		Effective (good and excellent) hemostasis 12 hours post-randomization as determined by the blinded EAC
Secondary Efficacy		
• Evaluate the effect of and versus usual care on anti-factivity		Percent change from baseline to nadir in anti-fXa activity during the first 2 hours post-randomization
Additional Efficacy		
• Evaluate the effect of and versus usual care on throm generation		Change from baseline in thrombin generation parameters (with ETP as the primary measure), obtained at 1 and 12 hours post-randomization
• Evaluate the effect of and versus usual care on neuro function		Proportion of neurologic deterioration, as defined by an NIHSS score increase ≥ 4 or a GCS score decrease ≥ 2 at 24 hours post-randomization versus baseline.
	•	Change from baseline in the mRS score at 30 days post-randomization.
	•	Change from baseline in the NIHSS score obtained at 2, 3, 6, 12, 24, and 72 hours post-randomization

Table 1:Objectives and Endpoints

Table 1:Object	tives and	Endpoints
----------------	-----------	-----------

Ob	jectives	En	dpoints
		•	Change from baseline in the GCS score obtained at 2, 3, 6, 12, 24, and 72 hours post-randomization
		•	Proportion of participants with $a \ge 7$ -point increase from baseline in the NIHSS score at 12 hours post-randomization
		•	Hemostatic efficacy evaluated using only imaging parameters
		•	Proportion of participants using rescue therapy and/or procedures between 3 and 12 hours post-randomization
•	Assess the relationship between anti-fXa activity and the achievement of effective hemostasis	•	Correlation analysis between anti-fXa activity and the achievement of effective hemostasis
•	• Evaluate the effect of and examet versus usual care on health-related		Health-related quality of life as assessed by the EQ-5D questionnaire at 30 days post-randomization
	quality of life	•	UW-mRS score at 30 days post-randomization
Sa	fety		

1.2. Study Design

This is a Phase 4, randomized, multicenter clinical study designed to determine the efficacy and safety of andexanet compared to usual care (UC) in participants presenting with acute ICrH (including intracerebral hemorrhage) within 6 hours of symptom onset (from the baseline imaging scan) and within 15 hours of taking an oral FXa inhibitor (from randomization). It should be noted that Protocol Amendment (PA) V1 modified Inclusion Criterion No. 3 to limit enrollment to participants with intracerebral hemorrhage to increase the homogeneity of the study population and to clarify eligible hematoma blood volume; consequently, there may be some nonintracerebral participants enrolled.

A summary of the study design can be found as below:

- The study will use a prospective, randomized, open-label design.
- Participants will be randomized 1:1 to receive either and exanet or UC stratified as follows, as detailed in PA V1:
 - Intended PCC use (yes versus no).
 - Time from symptom onset to the baseline imaging scan (< 180 minutes versus \geq 180 minutes).
- Randomization must occur within 15 hours following the last dose of the FXa inhibitor. For participants enrolled > 15 hours or where the last dose time of the FXa inhibitor is unknown, if a local anti-fXa activity level obtained within 2 hours after informed consent (as part of UC) and prior to randomization is > 100 ng/mL for direct FXa inhibitors (apixaban, rivaroxaban, and edoxaban), the participant may be enrolled, irrespective of the time of the last dose, and the participant will receive the high andexanet dosing regimen.
- UC will consist of any treatments (including no treatment) other than and exanet administered within 3 hours post-randomization that the Investigator and/or other treating physicians consider to be appropriate.
- For and example treatment, participants will receive 1 of 2 dosing regimens of and example based on which FXa inhibitor they receive and the amount and timing of the most recent dose, as indicated in Protocol Section 6.2. The and example and the gradient dosing regimens to be examined in this study are as follows:

- Low dose: 400 mg intravenous (IV) bolus, followed by a continuous infusion of 480 mg at 4 mg/min for 120 minutes.
- High dose: 800 mg IV bolus, followed by a continuous infusion of 960 mg at 8 mg/min for 120 minutes.
- Andexanet will be given via an IV bolus administered over approximately 15 minutes (low dose) to 30 minutes (high dose), followed immediately by a continuous infusion administered over approximately 120 minutes. There will be no crossover between treatment groups.
- The study duration for most participants will be up to 37 days. The study duration includes 3 study periods as follows:
 - Screening and Baseline Periods: < 1 day (Day 1)
 - Treatment Period: < 1 day (Day 1)
 - Follow-up Period (all adverse events [AEs], survival, and antibodies): 30 days (Day 1 to 30 study visit)

Participants with a positive anti-andexanet antibody response at the Day 30 visit will have an additional visit approximately 120 days post-randomization or within 30 days from when the positive test is made known to the Investigator, whichever is later.

- The primary efficacy endpoint is effective hemostasis (excellent or good versus poor/none versus nonevaluable), based on assessment of neurologic status determined by National Institutes of Health Stroke Scale (NIHSS), the use of rescue therapy, and hematoma expansion evaluation at 12 hours post-randomization by an imaging scan (computed tomography [CT] or magnetic resonance imaging [MRI]). Effective hemostasis will be determined by an adjudication algorithm or will be adjudicated by a blinded Endpoint Adjudication Committee (EAC). The derivation of effective hemostasis is provided in Section 6.1. Refer to separate Adjudication Charter for further information.
- The EAC will also adjudicate all thrombotic events (TEs), which are reported as AEs and all deaths. TEs are adverse events of special interest (AESIs) for the study.
- Approximately 900 participants are planned to be enrolled in the study at approximately 250 sites in North America, Europe, and Asia.
- A formal interim analysis for efficacy will be performed when approximately 50% (450 participants) of the anticipated sample size has been adjudicated. The main purposes of the interim analysis are 1) to assess whether to stop the study early due to efficacy and 2) to evaluate safety. Interim analysis will be performed by an independent statistics group and evaluated by the Data Safety Monitoring Board (DSMB). Details regarding the interim analysis are presented in Section 5.9.

A preplanned sample size re-estimation (SSR) will be performed by the DSMB-associated statistician to reassess the required size of the study population based on estimation of the primary endpoint at the interim analysis. If an increase is required, the total number of participants enrolled may be increased to 1200 participants (with an addition of 300 participants).

Statistical Analysis Plan ALXN2070 18-513 (Amendment 3)

There are 2 data cutoff (DCO) points in ANNEXA-I. The first DCO is for the planned interim analysis of the primary efficacy endpoint by the DSMB, after 50% of the anticipated patients have been adjudicated for effective hemostasis. If the DSMB recommend stopping the study based on the interim analysis results, the first DCO will be used for confirmatory analyses of efficacy endpoints (primary efficacy population, N = 450). Enrollment of patients will be continued without interruption from the first DCO until the stop decision is communicated; then recruitment will be closed which is the second DCO. The second DCO captures the data from all patients who participate in the study (extended population, N = 450 + X) and forms the basis for the safety analyses along with sensitivity analyses of the efficacy endpoints.

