10.5.3.1. Primary Efficacy Endpoint

The primary efficacy endpoint is based on the achievement of effective hemostasis 12 hours post-randomization, as determined by the blinded EAC, based on pre-specified criteria documented in the Adjudication Charter (see Appendix B).

Effective hemostasis will be further defined as:

- 1 = for patients with hemostatic efficacy rated by the EAC as excellent or good, and
- 0 = for patients with hemostatic efficacy rated by the EAC as poor/none.

For a patient to have excellent or good hemostatic efficacy, he or she must meet all of the following criteria:

- NIHSS score of less than +7 point change from the baseline score at 12 hours post-randomization.
- No greater than 35% increase from baseline in hematoma volume within 12 hours post-randomization.
- Has not received rescue therapy (as defined in Section 7.2, Section 7.3, and Section 7.4) between 3 and 12 hours post-randomization

If data supporting either the imaging or clinical components of the adjudication of hemostatic efficacy are missing, out-of-window, uninterpretable or confounded (e.g., intubation or sedation), cases will be referred for external adjudication by EAC. Procoagulant blood products administered within 3 hours post-randomization to patients randomized to andexanet will be reviewed by EAC to determine if they were related to clinical or administrative reasons. Surgeries or procedures impacting hematoma volume within 3 hours post-randomization will also be reviewed by EAC to determine if related to clinical or administrative reasons (see Section 7.2, Section 7.3, and Section 7.4).

Cases where it is determined that there is insufficient information, or when it is not otherwise possible to properly assess the effect of treatment, will be further classified by the EAC as 'non-evaluable due to administrative reasons' (e.g., follow-up scan not available/ performed/ interpretable, patient transferred to another facility for administrative purposes) or 'non-evaluable due to clinical reasons' (e.g., patient died, patient had unplanned surgery draining hematoma).

All ITT patients will be included in the primary analysis. Patients with non-evaluable hemostatic efficacy due to clinical reasons will be treated as treatment failures (similar to patients with poor/none hemostatic efficacy). Both non-evaluable subjects due to administrative and clinical reasons will be included in the denominator for primary efficacy analysis.

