10.7. Interim Analyses

One planned, formal interim analysis on the primary efficacy endpoint will be performed by the DSMB-associated statistician after 50% of the anticipated participants has been adjudicated for hemostatic efficacy. DSMB will evaluate the results and recommend altering or stopping the study in the event of prespecified efficacy. Enrollment will not be paused during the interim analysis.

10.7.1. Stopping Criterion Due to Efficacy at Interim

The overall type I error for the interim and final analysis is controlled at 5% by employing the alpha spending function by Lan and DeMets based on Pocock boundaries [6]. If the interim p-value < 0.0310 for comparing andexanet and usual care in the primary endpoint analysis, DSMB may recommend stopping the study. In this case, the efficacy results from the interim analysis (with 50% of the anticipated participants) will be used for regulatory communication and submission. Enrollment of patients will proceed without interruption while the analysis is ongoing, resulting in more than 50% of the anticipated participant in the final data cutoff; efficacy analysis on the final data cutoff will be considered as supportive.

10.7.2. Sample Size Re-estimation at Interim

If the DSMB recommendation at interim is to continue the study, a pre-planned sample size re-estimation (SSR) will be performed by the DSMB-associated statistician with the interim data. The SSR will be based on a conditional power (CP) of comparing and exanet and usual care at final (n=900) given the interim data, using a promising zone between 30% and 90% [31]. The assumption used for CP calculation is that the rate of hemostatic efficacy in and exanet and usual care at final is 80% and 70%, respectively. Based on the observed CP, DSMB will recommend:

- No increase in sample size, if the CP < 30% or > 90%;
- Increase the sample size to up to 1200 if $30\% \le CP \le 90\%$.

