5.9. Interim Analyses

One planned, formal interim analysis on the primary efficacy endpoint will be performed by the DSMB-associated statistician after 50% of the anticipated participants has been adjudicated for hemostatic efficacy. DSMB will evaluate the results and recommend altering or stopping the study in the event of efficacy. Enrollment will not be paused during the interim analysis.

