The majority of cases will not require review by adjudicators as the outcome rating will be obvious based on the core laboratory interpretation, NIHSS scores, and lack of additional treatments or procedures. An algorithm will be applied to the data from the imaging core laboratory and information provided by the sites on CRFs. The algorithm will determine if the case can be immediately classified as excellent, good, or poor/none or whether the case requires review by adjudicators and additional review by the EAC. Cases will be referred for EAC review, if the change in hematoma volume is < 35% and the change in the NIHSS score between baseline and 12 hours is < 7 and if one of the following criteria is met:

- baseline or 12-hour scans (11 to 15 hours post-randomization) missing, uninterpretable, or fall outside the collection window.
- NIHSS scores missing or fall outside the collection window for either baseline or 12-hour evaluations.
- Cases where the blinded imaging core laboratory readers indicate that review by the EAC is needed (or 3 readers disagree on classification of hematoma volume change).
- Cases where the participant was either sedated or intubated for either baseline or 12-hour NIHSS assessment (or both).
- Documented procedures that could potentially drain hematoma between 3- and 12hours post-randomization.
- Cases, where it is determined that there is insufficient information or where it is not otherwise possible to properly assess the effect of treatment, will be further classified by the EAC as follows:
 - Nonevaluable due to administrative reasons (eg, follow-up scans not available/performed/interpretable and the participant transferred to another

facility for administrative purposes); these participants will be analyzed as having poor/none effective hemostasis.

• Nonevaluable due to clinical reasons (eg, the participant died and the participant had unplanned surgery draining hematoma); these participants will be analyzed as having poor/none effective hemostasis.

Identifying Rescue Medications/Procedures

Rescue medications are identified from the concomitant medication CRF pages based on the following:

- 1. If indication for medication is "TO ACHIEVE HEMOSTASIS FOR CONTINUOUS (WORSENING) INTRACEREBRAL HEMORRHAGE BLEED," "TO ACHIEVE HEMOSTASIS FOR INITIAL BLEED," or "TO ACHIEVE HEMOSTASIS FOR NEW BLEED RE-BLEED" (except for tranexamic acid, which is permitted regardless of indication).

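### The interim set of 450, confirmatory if the trial stops, is triggered by a count of completed adjudications; the plan does not say which patients belong to it or what happens to open EAC cases

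*SAP*

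**What the plan says.** **Trigger.** The SAP's design list (1.2) schedules the interim "when approximately 50% (450 participants) of the anticipated sample size has been adjudicated". Its data-cutoff paragraph says "after 50% of the anticipated patients have been adjudicated for effective hemostasis", and Protocol 10.7 says "after 50% of the anticipated participants has been adjudicated for hemostatic efficacy". All three count completed adjudications; none refers to order or date of randomisation.

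**Role of the set.** If the DSMB recommends stopping, SAP 1.2 states that "the first DCO will be used for confirmatory analyses of efficacy endpoints (primary efficacy population, N = 450". Protocol 10.7.1 and SAP 5.9.1 use these results for regulatory submission. The later cutoff with all patients is supportive (protocol) or a sensitivity analysis (SAP).

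**Recruitment.** SAP 5.9: "Enrollment will not be paused during the interim analysis". Randomised but unadjudicated patients can therefore exist at the cutoff.

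**Two adjudication routes.** SAP 6.1: "The majority of cases will not require review by adjudicators as the outcome rating will be obvious". The remainder go to adjudicators and the EAC. They include cases with missing or out-of-window scans or NIHSS, sedation or intubation, core-laboratory disagreement, and procedures that might drain the hematoma.

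**Population.** Protocol 10.5.3.1 and SAP 5.3 put the primary analysis on ITT. Under the SAP, non-evaluable patients count as poor/none, but only once the EAC has classified them.

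**If the trial continues.** Protocol 10.7.3 and SAP 5.9.3 combine a stage 1 statistic on 450 patients with a stage 2 statistic on later participants when the sample size is increased to 1200.

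**The concern.** How fast a case is adjudicated depends on what happened after randomisation. A clean scan and NIHSS can be rated at once; a patient who was sedated, missed the scan or had a procedure waits for review. If the set is filled in order of completed adjudications, it over-represents straightforward cases, and a pending patient escapes the rule that would count a non-evaluable outcome as a failure. That is selection on a post-randomisation event in an analysis declared to be ITT.

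The trial is open-label and some referral rules differ by arm, for example: "Procoagulant blood products administered within 3 hours post-randomization to patients randomized to andexanet will be reviewed by EAC". Balance in open cases therefore cannot be assumed. The analysis at stake can stop the trial and would then be the confirmatory result.

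The gap also matters if the trial continues. The text does not say which stage holds a patient randomised before the cutoff but adjudicated after it, yet the weighted statistic needs that split to be fixed independently of outcome.

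**Working it through.** **1. The plan's own figure.** Pocock-type spending at half information is 0.05 × ln(1 + (e − 1) × 0.5) = 0.0310, as stated. With the final level of 0.0277 the overall two-sided error is 0.0500. The plan's alpha is correct. The interim error in favour of andexanet is 0.0310/2 = 1.55%, and the critical z is 2.157.

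**2. Model for omission.** Let p be the true success rate in an arm, s the share of the arm open at the cutoff, and q the success rate among open cases. The rate among those counted is r = (p − s·q)/(1 − s), with s = referral rate × fraction of referrals still open.

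**3. Inputs.** From the documents: 450 patients, 1:1, so about 225 per arm, tested at 0.0310. Assumed, because the documents give neither referral rates nor adjudication lag: no true effect with p = 75% in both arms (midway between the planned 70% and 80%), and q = 40%. Referral and open fractions are varied.

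**4. Worked case: referral 20% andexanet, 10% usual care, half open.**
- Andexanet: s = 0.10, r = (0.75 − 0.04)/0.90 = 78.89%.
- Usual care: s = 0.05, r = (0.75 − 0.02)/0.95 = 76.84%.
- Spurious difference: +2.05 points.
- Standard error: √(2 × 0.7787 × 0.2213/225) = 0.0391.
- Effective threshold: 2.157 − 0.0205/0.0391 = 1.63, so the one-sided error is 5.1%.

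**5. Range (nominal 1.55%).**

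| Referral, andexanet vs usual care | Fraction open | Spurious difference (points) | One-sided interim error |
|---|---|---|---|
| 10% vs 10% | any | 0 | 1.55% |
| 15% vs 10% | 5% | +0.09 | 1.64% |
| 15% vs 10% | 10% | +0.18 | 1.73% |
| 20% vs 10% | 5% | +0.18 | 1.73% |
| 20% vs 10% | 10% | +0.36 | 1.93% |
| 15% vs 10% | 50% | +1.0 | 2.8% |
| 20% vs 10% | 50% | +2.05 | 5.1% |
| 10% vs 15% | 10% | −0.18 | 1.39% |
| 10% vs 15% | 50% | −1.0 | 0.8% |

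An observed difference of about 8.8 points (2.157 × 0.0408) is needed to cross the interim boundary.

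**6. What drives it.** If referred cases succeed at the overall 75%, r = p and there is no bias at any referral rate. Equal pending shares protect the error rate only if outcomes among open cases are also equal. For example, with true rates of 70% in both arms and 5% pending in each, but success among open cases of 20% (andexanet) versus 60% (usual care), the difference is +2.1 points and the error 4.8%.

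**7. After the fix.** With 450 patients fixed by randomisation order and all adjudicated, N stays 450, alpha stays 0.0310, and interim power for 80% versus 70% is 61.6%. Only the rule for who is counted changes.

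**The case against.** The strongest reply is that the quoted sentences set when the cutoff happens, not who is in it. Cutting at the first 450 randomised, once all are adjudicated, fits the text equally well and would be ITT. Interim and adjudication details are delegated to charters that are not in the documents. This stands: omission is permitted by the wording, not shown.

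A reader might also infer that open cases are mostly failures and that their loss favours andexanet. The documents do not support either inference.
- Under SAP 6.1, referral presupposes a volume change below 35% and an NIHSS change below 7. Known failures on those criteria are rated by algorithm and are not pending, and the EAC may rate a referred case effective.
- Referral rules exist in both arms. Protocol 7.2.3 and SAP 5.3.1 also send andexanet given in the usual care arm to the EAC. Protocol 7.2.4 sends early hemostatic agents for review with no arm restriction, and these are permitted in usual care but discouraged for andexanet without hematoma expansion. Protocol 7.3 reviews early surgery in both groups. The net direction is unknown.

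Having half of all referrals open is an extreme input. The endpoint is at 12 hours. Patients were enrolled before Amendment 1 (April 2020), and the April 2023 SAP still describes the cutoff as future, so only recent cases would normally be unresolved. This also stands, and makes the 5–10% rows the more realistic ones, though no turnaround time is given.

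Finally, the second cutoff counts everyone. That helps, but as a sensitivity analysis it does not replace the confirmatory result. It also does not settle the stage split.

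**Conclusion.** The point holds as a gap in the definition of a confirmatory population. The trigger is a count of adjudications, enrollment continues, the resulting 450 become confirmatory on stopping, and nothing fixes membership or the handling of open EAC reviews. Read literally, the rule allows a post-randomisation exclusion that conflicts with ITT and leaves stage 1 and stage 2 undefined.

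The documents do not show that slow cases are left out, nor that any omission would favour andexanet. The size rests on assumed referral rates, open fractions and a 40% success rate among referred cases. With referral higher in the andexanet arm, the one-sided interim error is about 1.6–1.9% when 5–10% of referrals are open and 2.8–5.1% when half are, against 1.55%. It is unchanged when pending shares and outcomes are equal, and below nominal when the imbalance is reversed. The likely effect is small. The reason to act is that membership should not be left open to a decision after data exist, and that closing the gap costs almost nothing.

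**What to change.** State in the SAP and the DSMB charter that:
- the interim set, which is also stage 1, is the first 450 consecutively randomised ITT patients by randomisation date and time (ITT, because patients randomised without ever signing consent are excluded from that set);
- the interim is run only when all 450 have a final adjudication;
- every later-randomised patient belongs to stage 2, whatever the date of adjudication;
- the number of these 450 still open when the count of 450 adjudications was reached is reported by arm, to the DSMB at the interim and in the study report.

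Cost: about one sentence in each document and a short wait for the last EAC cases. N = 450 and the 0.0310 level are unchanged. Including everyone randomised by the cutoff date instead would require the spent alpha to be recomputed (0.0315 at 460 patients, 0.0323 at 475, 0.0335 at 500), so fixing the first 450 is simpler.
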